9.4.2. Secondary efficacy indicators

9.4.2.1. The first relapse survival analysis after enrollment

Table 20. The time of the first relapse after enrollment

Items	Indicator	FAS		PPS	
		Experimental group	Control group	Experimental group	Control group
The time of the first relapse after enrollment (days)	N (Missing)				
	Mean (SD)				
	Median				
	Q1, Q3				
	Min, Max				
	95%CI				
	P-value				

Note: The time of first relapse after enrollment (days) = Date of first relapse after enrollment - Random date + 1.

Table 21. The first relapse survival analysis after enrollment

Items	Indicator	FAS		PPS	
		Experimental group	Control group	Experimental group	Control group
The time of the first relapse after enrollment (days)	N (Missing)				
	Endpoint event (%)(%)				
	Censoring (%)				
	Median survival time				
	95%CI				
	Q1, Q3				
	Log-rank test				
Cox regression analysis	Hazard Ratio				
	95%CI				
	Wald Chi-square				
	P-value				

9.4.2.2. 6-month relapse-free survival analysis after enrollment

Table 22. 6-month relapse-free survival analysis after enrollment

Items	Indicator	FAS		PPS	
		Experimental group	Control group	Experimental group	Control group
6-month recurrence time (days)	N (Missing)				
	Endpoint event (%)(%)				
	Censoring (%)				
	Median survival time				
	95%CI				
	Q1, Q3				
	Log-rank test				
Cox regression analysis	Hazard Ratio				
	95%CI				
	Wald Chi-square				
	P-value				

Figure 3. 6-month relapse-free survival analysis chart (FAS)

Figure 4. 6-month relapse-free survival analysis chart (PPS)

9.4.2.3. Serum renal function

Table 23. Changes in eGFR relative to baseline at each visit

Items	Indicator	FAS			PPS		
		Experimental group	Control group	Total	Experimental group	Control group	Total
Baseline	N (Missing)						
	Mean (SD)						
	Median						
	Q1, Q3						
	Min, Max						
	95%CI						
Between-group comparison in baseline	Statistics						
	P-value						
Visit 2/Day 7±3	N (Missing)						
	Mean (SD)						
	Median						
	Q1, Q3						
	Min, Max						
	95%CI						
Between-group comparison in Visit 2/Day 7±3	Statistics						
	P-value						
Change in Visit 2/Day 7±3 from baseline	N (Missing)						
	Mean (SD)						
	Median						
	Q1, Q3						
	Min, Max						
	95%CI						
Pre- and post-treatment comparison of intra-group	Statistical method						
	Statistics						
	P-value						
Comparison of changes between groups pre- and post-treatment	Statistics						
	P-value						
Visit 4/Day 56±7	N (Missing)						
	Mean (SD)						

Items	Indicator	FAS			PPS		
		Experimental group	Control group	Total	Experimental group	Control group	Total
	Median						
	Q1, Q3						
	Min, Max						
	95%CI						
Between-group comparison in Visit 4/Day 56±7	Statistics						
	P-value						
Change in Visit 4/Day 56±7 from baseline	N (Missing)						
	Mean (SD)						
	Median						
	Q1, Q3						
	Min, Max						
	95%CI						
Pre- and post-treatment comparison of intra-group	Statistical method						
	Statistics						
	P-value						
Comparison of changes between groups pre- and post-treatment	Statistics						
	P-value						
Visit 5/Day 112±7	N (Missing)						
	Mean (SD)						
	Median						
	Q1, Q3						
	Min, Max						
	95%CI						
Between-group comparison in Visit 5/Day 112±7	Statistics						
	P-value						
Change in Visit 5/Day 112±7 from baseline	N (Missing)						
	Mean (SD)						
	Median						
	Q1, Q3						
	Min, Max						
	95%CI						

Items	Indicator	FAS			PPS		
		Experimental group	Control group	Total	Experimental group	Control group	Total
Pre- and post-treatment comparison of intra-group	Statistical method						
	Statistics						
	P-value						
Comparison of changes between groups pre- and post-treatment	Statistics						
	P-value						
Visit 6/Day 168±7	N (Missing)						
	Mean (SD)						
	Median						
	Q1, Q3						
	Min, Max						
	95%CI						
Between-group comparison in Visit 6/Day 168±7	Statistics						
	P-value						
Change in Visit 6/Day 168±7 from baseline	N (Missing)						
	Mean (SD)						
	Median						
	Q1, Q3						
	Min, Max						
	95%CI						
Pre- and post-treatment comparison of intra-group	Statistical method						
	Statistics						
	P-value						
Comparison of changes between groups pre- and post-treatment	Statistics						
	P-value						
Visit 7/Day 224±7	N (Missing)						
	Mean (SD)						
	Median						
	Q1, Q3						
	Min, Max						
	95%CI						
Between-group comparison in Visit 7/Day 224±7	Statistics						

Items	Indicator	FAS			PPS		
		Experimental group	Control group	Total	Experimental group	Control group	Total
Change in Visit 7/Day 224±7 from baseline	P-value						
	N (Missing)						
	Mean (SD)						
	Median						
	Q1, Q3						
	Min, Max						
	95%CI						
Pre- and post-treatment comparison of intra-group	Statistical method						
	Statistics						
	P-value						
Comparison of changes between groups pre- and post-treatment	Statistics						
	P-value						
Visit 8/Day 280±7	N (Missing)						
	Mean (SD)						
	Median						
	Q1, Q3						
	Min, Max						
	95%CI						
Between-group comparison in Visit 8/Day 280±7	Statistics						
	P-value						
Change in Visit 8/Day 280±7 from baseline	N (Missing)						
	Mean (SD)						
	Median						
	Q1, Q3						
	Min, Max						
	95%CI						
Pre- and post-treatment comparison of intra-group	Statistical method						
	Statistics						
	P-value						
Comparison of changes between groups pre- and post-treatment	Statistics						
	P-value						

Items	Indicator	FAS			PPS		
		Experimental group	Control group	Total	Experimental group	Control group	Total
Visit 9/Day 364±7	N (Missing)						
	Mean (SD)						
	Median						
	Q1, Q3						
	Min, Max						
	95%CI						
Between-group comparison in Visit 9/Day 364±7	Statistics						
	P-value						
Change in Visit 9/Day 364±7 from baseline	N (Missing)						
	Mean (SD)						
	Median						
	Q1, Q3						
	Min, Max						
	95%CI						
Pre- and post-treatment comparison of intra-group	Statistical method						
	Statistics						
	P-value						
Comparison of changes between groups pre- and post-treatment	Statistics						
	P-value						

Figure 5. Quantitative variables of eGFR at each visit

Table 24. Change in Scr from baseline at each visit

Ibid. Same below.

Figure 6. Quantitative variables of Scr at each visit

Table 25. Change in serum uric acid from baseline at each visit

Figure 7. Quantitative variables of serum uric acid at each visit

Table 26. Change in blood urea nitrogen from baseline at each visit

Figure 8. Quantitative variables of blood urea nitrogen at each visit

Table 27. Change in serum cystatin C from baseline at each visit

Figure 9. Quantitative variables of serum cystatin C at each visit

9.4.2.4. Cumulative steroid dosage

Table 28. Total amount of steroids taken during the study

Items	Indicator	Experimental group	Control group	Total
Total amount of steroids taken during the study	N (Missing)			
	Mean (SD)			
	Median			
	Q1, Q3			
	Min, Max			
	Statistics			
	P-value			

Table 29. Total amount of steroids taken during 6 months after enrollment

Items	Indicator	Experimental group	Control group	Total
Total amount of steroids taken during 6 months after enrollment	N (Missing)			
	Mean (SD)			
	Median			
	Q1, Q3			
	Min, Max			

Items	Indicator	Experimental group	Control group	Total
	Statistics			
	P-value			

9.4.2.5. Vital signs

Table 30. Change in systolic blood pressure from baseline at each visit

Table 31. Change in diastolic blood pressure from baseline at each visit

Table 32. Change in height from baseline at each visit

Table 33. Change in weight from baseline at each visit

Table 34. Height percentile

Items	Indicator	Experimental group	Control group	Total
Baseline	N (Missing)			
	Mean (SD)			
	Median			
	Q1, Q3			
	Min, Max			
	Statistics			
	P-value			
Visit 5/Day 112±7	N (Missing)			
	Mean (SD)			
	Median			
	Q1, Q3			
	Min, Max			
	Statistics			
	P-value			
Visit 9/Day 364±7	N (Missing)			
	Mean (SD)			
	Median			

Items	Indicator	Experimental group	Control group	Total
	Q1, Q3			
	Min, Max			
	Statistics			
	P-value			

Note: Data from the external file “XX”.

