4.1 Inclusion criteria

Only those who meet all the conditions listed in this column can be considered for inclusion in this research:

- (1) Steroid-sensitive nephrotic syndrome with frequent relapse (FRNS) or steroid dependence (SDNS);
- (2) Age: 2-18 years old;
- (3) Normal renal function: $eGFR \geq 90 \text{ mL/min/1.73m}^2$;
- (4) At the time of enrollment, urinary protein $< 1+$ or urinary protein/creatinine $< 0.2 \text{ g/g}$ ($< 20 \text{ mg/mmol}$) in the morning for 3 consecutive days or more;
- (5) No use of tacrolimus, mycophenolate mofetil, cyclosporine A, rituximab or cyclophosphamide within 2 years before enrollment;

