7.2 Efficacy evaluation

7.2.1 Primary observation outcomes: 1-year relapse-free survival

7.2.2 Secondary observation outcomes:

- (1) Frequency of relapses; the time of the first relapse after enrollment; relapse-free **survival** in the first six months after enrollment;
- (2) Renal function: Serum creatinine and glomerular filtration rate (eGFR, see Appendix 1 for the calculation method)
- (3) Cumulative steroid dosage: The total amount of steroids taken during this research and the total amount of steroids in the first half of the year
- (4) Others: Blood pressure (see Appendix 2 for details), height, weight, blood lipid, hemoglobin, blood albumin, urinary protein/creatinine (morning urine), etc.
- (5) Adverse reaction
- (6) 24hr urinary protein quantification (applicable to subjects > 3 years old)

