Appendix 2 Blood pressure reference values for children

Boy

Age		Diastolic blood pressure, mmHg												
		Systolic blood pressure, mmHg							Height percentile					
		Height percentile												
5th	10th	25th	50th	75th	90th	95th	5th	10th	25th	50th	75th	90th	95th	
	98	99	101	103	104	106	106	54	54	55	56	57	58	58
2	101	102	104	106	108	109	110	59	59	60	61	62	63	63
3	104	105	107	109	110	112	113	63	63	64	65	66	67	67
4	106	107	109	110	112	114	115	66	67	68	69	70	71	71
5	108	109	110	112	114	115	116	69	70	71	72	73	74	74
6	109	110	112	114	115	117	117	72	72	73	74	75	76	76
7	110	111	113	115	117	118	119	74	74	75	76	77	78	78
8	111	112	114	116	118	119	120	75	76	77	78	79	79	80
9	113	114	116	118	119	121	121	76	77	78	79	80	81	81
10	115	116	117	119	121	122	123	77	78	79	80	81	81	82
11	117	118	119	121	123	124	125	78	78	79	80	81	82	82
12	119	120	122	123	125	127	127	78	79	80	81	82	82	83
13	121	122	124	126	128	129	130	79	79	80	81	82	83	83
14	124	125	127	128	130	132	133	80	80	81	82	83	84	84
15	126	127	129	131	133	134	135	81	81	82	83	84	85	85
16	129	130	132	134	135	137	137	82	83	83	84	85	86	87
17	131	132	134	136	138	139	140	84	85	86	87	87	88	89

Girl

Age	Systolic blood pressure, mmHg							Diastolic blood pressure, mmHg						
	Height percentile							Height percentile						
	5th	10th	25th	50th	75th	90th	95th	5th	10th	25th	50th	75th	90th	95th
1	100	101	102	104	105	106	107	56	57	57	58	59	59	60
2	102	103	104	105	107	108	109	61	62	62	63	64	65	65
3	104	104	105	107	108	109	110	65	66	66	67	68	68	69
4	105	106	107	108	110	111	112	68	68	69	70	71	71	72
5	107	107	108	110	111	112	113	70	71	71	72	73	73	74
6	108	109	110	111	113	114	115	72	72	73	74	74	75	76
7	110	111	112	113	115	116	116	73	74	74	75	76	76	77
8	112	112	114	115	116	118	118	75	75	75	76	77	78	78
9	114	114	115	117	120	121	122	77	77	77	78	79	80	80
10	116	116	117	119	120	121	122	77	77	77	78	79	80	80
11	118	118	119	121	122	123	124	78	78	78	79	80	81	81
12	119	120	121	123	124	125	126	79	79	79	80	81	82	82
13	121	122	123	124	126	127	128	80	80	80	81	82	83	83
14	123	123	125	126	127	129	129	81	81	81	82	83	84	84
15	124	125	126	127	129	130	131	82	82	82	83	84	85	85
16	125	126	127	129	130	131	132	82	82	83	84	85	85	86
17	125	126	127	129	130	131	132	82	83	83	84	85	85	86

The blood pressure at 95th percentile standard¹⁴

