6.2. Efficacy evaluation

6.2.1. Primary observation outcomes: 1-year relapse-free survival

6.2.2. Secondary observation outcomes:

- (1) Frequency of relapses; the time of the first relapse after enrollment; relapse-free survival in the first six months after enrollment;
- (2) Renal function: Serum creatinine and glomerular filtration rate (eGFR, see Appendix 1 for the calculation method)
- (3) Cumulative steroid dosage: The total amount of steroids taken during this research and the total amount of steroids in the first half of the year
- (4) Others: Blood pressure (see Appendix 2 for details), height, weight, blood lipid, hemoglobin, blood albumin, urinary protein/creatinine (morning urine), etc.
- (5) Adverse reaction
- (6) 24hr urinary protein quantification (applicable to subjects > 3 years old)

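### The SAP's blood pressure outcome refers to the Appendix 2 95th-percentile table, but no SAP table uses it, so the plan yields no age-referenced blood pressure result or hypertension rate

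*SAP*

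**What the plan says.** SAP 6.2.2(4) lists the outcome as "Others: Blood pressure (see Appendix 2 for details), height, weight, blood lipid, hemoglobin, blood albumin", and Protocol 7.2.2(4) has the same reference. Appendix 2, printed in the protocol, gives systolic and diastolic limits by sex, age and height percentile, labelled "The blood pressure at 95th percentile standard".

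In SAP 9.4.2.5 the blood pressure tables are "Change in systolic blood pressure from baseline at each visit" (Table 30) and "Change in diastolic blood pressure from baseline at each visit" (Table 31). A note under Table 24 carries the Table 23 layout forward: values by visit, change from baseline, within-arm tests and between-arm tests. SAP 8.1.4 sends secondary outcomes to the general methods of SAP 7.2.2, which for quantitative data means a t-test or Wilcoxon rank sum test.

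Height appears twice in the same section. Table 32 is "Change in height from baseline at each visit". "Table 34. Height percentile" compares percentiles between arms at baseline, Visit 5 and Visit 9, each with a statistic and P-value. Its source is an external file named only by the placeholder XX.

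The inclusion criterion is "Age: 2-18 years old".

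**The concern.** The outcome definition points to a reference table that the analysis never uses. Whether a given mmHg value is high depends on the child's age, sex and height, and this trial spans almost the whole paediatric range. Followed as written, the plan ends with mean mmHg by arm and no statement of how many children exceeded the limit the documents themselves supply.

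This matters for the comparison being made. Protocol 8.1.1 lists hypertension as very common with tacrolimus, and the protocol background names hypertension and growth inhibition among the harms of long-term steroids. After baseline, Tables 30 and 31 are the only measured blood pressure output, because the safety vital signs (Tables 67 and 68) are heart rate and respiratory rate. Antihypertensive treatment is allowed, so treated children can pull the arm mean down, and no table shows blood pressure together with that treatment.

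**Working it through.** The plan states no effect size, standard deviation or event rate for blood pressure or height, so there is no figure of its own to reproduce.

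**1. Is Appendix 2 used anywhere?** These are the SAP outputs that could use it:

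| SAP output | Content | Uses Appendix 2? |
|---|---|---|
| Table 5 | Baseline systolic and diastolic mmHg | No |
| Tables 30–31 | mmHg and change by visit | No |
| Tables 65–66 | Coded adverse events and reactions | No threshold stated |
| Tables 67–68 | Heart rate, respiratory rate | Not blood pressure |

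No table classifies a child, gives a blood pressure percentile or counts children above the limit.

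**2. Can a rate be recovered from mean mmHg?** Appendix 2, boys at the 50th height percentile:

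| Age | Systolic 95th percentile (mmHg) |
|---|---|
| 2 | 106 |
| 4 | 110 |
| 7 | 115 |
| 12 | 123 |
| 17 | 136 |

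A reading of 118 mmHg is 118 − 110 = 8 above the cut-off at age 4 and 123 − 118 = 5 below it at age 12. The arm mean does not determine how many children are over their own limit.

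**3. Does age distort the change comparison?** A change score removes each child's starting level. What remains is drift over one year. Between adjacent ages from 2 to 17, the boys' systolic cut-off moves by +1 to +3 mmHg (mean 2.0) and the girls' by 0 to +4 (mean 1.5). Under 1:1 randomisation the expected drift is the same in both arms, so it does not bias the between-arm difference.

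**4. What would baseline adjustment gain?** Assume equal variance σ² at baseline and follow-up, with within-arm correlation r.

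- Change score: variance 2σ²(1 − r).
- ANCOVA on baseline: variance σ²(1 − r²).
- Ratio: (1 − r²) / [2(1 − r)] = (1 + r)/2.
- Table 34 has no change row, so its comparator is the Visit 9 value alone, with variance σ². There the ratio is 1 − r².

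| Assumed r | ANCOVA / change, (1+r)/2 | ANCOVA / Visit 9 value alone, 1−r² |
|---|---|---|
| 0.5 | 0.75 | 0.75 |
| 0.7 | 0.85 | 0.51 |
| 0.9 | 0.95 | 0.19 |

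The documents give no r. These ratios cover adjustment for baseline only.

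**5. Is Appendix 2 ready to use?** Not quite. It stops at age 17 while inclusion runs to 18. The girls' age-9 row equals the age-10 row in 10 of 14 cells: systolic at the 75th, 90th and 95th height percentiles (120, 121, 122) and all seven diastolic values. The other four systolic cells differ (114, 114, 115, 117 against 116, 116, 117, 119).

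**The case against.** The listed outcomes are blood pressure and height. Neither document names the proportion hypertensive as an outcome, and a randomised comparison of change is valid without any reference table. A reader might infer that raw mmHg and raw height cannot show a drug effect at all. The documents do not support that: Tables 30 and 31 can show a between-arm shift in mean blood pressure, and Table 34 already offers a valid percentile comparison at Visits 5 and 9. The growth point is therefore about precision and an unnamed reference.

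A reader might also take the spread of the cut-offs from age 2 to 17 (boys at median height, 106/61 to 136/87, or 30/26 mmHg) as noise in the analysis. It is a difference between children of different ages and largely cancels in a change score. Nor does the SAP depart from the protocol's definition: both carry the Appendix 2 reference, and the gap is between SAP 6.2.2(4) and the SAP's own tables.

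Hypertension also has another route. Protocol 8.3 has worsening vital signs that meet the adverse-event criteria reported as adverse events, and Tables 65 and 66 compare coded events between arms. That stands in part. No blood pressure threshold is given and investigators know the allocation, so this route does not replace a count against a fixed cut-off.

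Finally, the gain over change scores may be small. Across ages 2 to 18, age drives both measurements and r may be high; at an assumed 0.9 the variance falls by only 5%.

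**Conclusion.** The point holds for blood pressure and, more narrowly, for growth. The SAP refers to Appendix 2 in its outcome definition and never applies it. The planned tables validly compare mean shift but leave out an age-, sex- and height-referenced result and any hypertension rate based on a stated limit. Growth is covered by Table 34, with two weaknesses: no adjustment for baseline percentile and no named source or growth reference.

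The missing classification is a gap in reporting, and no numerical bias is claimed. The precision gain from ANCOVA over change scores is a variance reduction of 25%, 15% or 5% at assumed r of 0.5, 0.7 or 0.9, given equal variances. The primary relapse analysis is unaffected.

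**What to change.** 1. Add a table, by visit and arm, of the number and percentage of children with systolic or diastolic pressure at or above the Appendix 2 95th percentile. The chi-square or exact test in SAP 7.2.2 already covers the comparison. Report antihypertensive use alongside.
2. Before programming, settle the lookup: check the girls' age-9 row against its source, state a rule for age 18, name the height-percentile reference, and say how children between height columns are classified. Use age at the visit; SAP section 8 defines age only at consent.
3. Compare systolic and diastolic pressure by ANCOVA on baseline value, age and sex. Compare Visit 9 height percentile, or preferably SD score, by ANCOVA on its baseline value, and replace the placeholder source in Table 34 with the actual file and growth reference. ANCOVA is in the SAP's abbreviation list but in none of its methods.

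The cost is extra programming and deriving a height percentile at each visit, where Table 34 needs only three. Age, sex, height and vital signs are already collected under the flow chart, so no new measurement is needed; the growth reference has to be supplied.

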9.4.2.6. Blood lipid

Table 35. Change in triglyceride from baseline at each visit

Table 36. Change in total cholesterol from baseline at each visit

9.4.2.7. Haemoglobin and albumin (ALB)

Table 37. Change in haemoglobin from baseline at each visit

Table 38. Change in ALB from baseline at each visit

9.4.2.8. Urine test

Table 39. Change in 24hr urine protein (>3 years old) from baseline at each visit

Table 40. Change in urine protein/creatinine (morning urine) from baseline at each visit

9.4.2.9. Serum liver function and fasting blood glucose

Table 41. Change in glutamyl transpeptidase (GT) from baseline at each visit

Table 42. Change in alanine aminotransferase (ALT) from baseline at each visit

Table 43. Change in aspartate aminotransferase (AST) from baseline at each visit

Table 44. Change in lactate dehydrogenase from baseline at each visit

Table 45. Change in total bilirubin from baseline at each visit

Table 46. Change in direct bilirubin from baseline at each visit

Table 47. Change in alkaline phosphatase from baseline at each visit

Table 48. Change in total protein from baseline at each visit

Table 49. Change in globulin from baseline at each visit

Table 50. Change in fasting blood glucose from baseline at each visit

9.4.2.10. Blood routine examination

Table 51. Change in leukocyte count (WBC) from baseline at each visit

Table 52. Change in erythrocyte count (RBC) from baseline at each visit

Table 53. Change in platelet count (PLT) from baseline at each visit

Table 54. Change in lymphocyte percentage (LY) from baseline at each visit

9.4.2.11. Urine routine examination

Table 55. Change in leukocyte from baseline at each visit

Table 56. Change in erythrocyte from baseline at each visit

Table 57. Change in pH from baseline at each visit

Table 58. Change in urine protein from baseline at each visit

9.4.2.12. Plasma concentration

Table 59. Change in tacrolimus concentration in plasma from baseline at each visit

Table 60. Change in mycophenolic acid concentration in plasma from baseline at each visit

9.4.3. Disease remission

Table 61. Disease remission at each visit

Items	Indicator	Experimental group	Control group	Total
Visit 1/Day 0	Complete remission (CR) n (%)			
	Partial remission (PR) n (%)			
	Non remission (NR) n (%)			
	Total (Missing)			
	Statistics			
	P-value			
Visit 2/Day 7±3	Complete remission (CR) n (%)			

Partial remission (PR) n (%)

Non remission (NR) n (%)

Total (Missing)

Statistics

P-value

...

9.5. Safety analysis (SS)

9.5.1. Adverse event (AE)

Table 62. Between-group comparison of AE

Items	Experimental group			Control group			P-value
	No. of AEs	No. of subjects	Percentage	No. of AEs	No. of subjects	Percentage	
AE							
AE of severe severity							
Drug-related AE							
Serious adverse event (SAE)							
Drug-related SAE							
Drop-out due to AE							
Drop-out due to SAE							

Note 1: The definitions related to drugs are “definitely related”, “probably related”, “possibly related”, “unlikely related” and “not related”.

Note 2: The data of SAE that cause the drop-out came from the external file “XX”.

Table 63. characteristics of AE in each group

Items	Experimental group			Control group			P-value
	No. of AEs	No. of subjects	Incidence	No. of AEs	No. of subjects	Incidence	
Relationship with study drug							
Definitely related							
Probably related							

Items	Experimental group			Control group			P-value
	No. of AEs	No. of subjects	Incidence	No. of AEs	No. of subjects	Incidence	
Possibly related							
Unlikely related							
Not related							
Outcome	Recovered/resolved						
	Recovered/resolved with sequelae						
	Not recovered						
	Recovering/resolving						
	Death						
	Unknown						

Table 64. Between-group comparison of SAE

Items	Experimental group (n=XX)			Control group (n=XX)			Total (n=XX)	P-value
	No. of AEs	No. of subjects	Incidence (%)	No. of AEs	No. of subjects	Incidence (%)		
Results in death								
Requires hospitalization								
Prolongs hospitalization								
Disability								
Dysfunction								
Congenital malformation								
Life threatening								
Other								

Table 65. Summary of AE base on SOC and PT coding

Indicator	Experimental group (n=XX)			Control group (n=XX)			Total (n=XX)	P-value
	No. of AEs	No. of subjects	Incidence (%)	No. of AEs	No. of subjects	Incidence (%)		
AE								

Indicator	Experimental group (n=XX)			Control group (n=XX)			Total (n=XX)			P-value
	No. of AEs	No. of subjects	Incidence (%)	No. of AEs	No. of subjects	Incidence (%)	No. of AEs	No. of subjects	Incidence (%)	
SOC1										
PT1										
PT2										
...										
SOC2										
PT1										
PT2										
...										

Table 66. Summary of adverse reactions base on SOC and PT coding

Indicator	Experimental group (n=XX)			Control group (n=XX)			Total (n=XX)			P-value
	No. of AEs	No. of subjects	Incidence (%)	No. of AEs	No. of subjects	Incidence (%)	No. of AEs	No. of subjects	Incidence (%)	
Adverse event										
SOC1										
PT1										
PT2										
...										
SOC2										
PT1										
PT2										
...										

